Study Protocol

Feasibility of Home Monitoring after Primary Total Knee Arthroplasty

Principal Investigator: [name]

Email: [contact]

Background

Over one million primary total hip and total knee arthroplasties (TKAs) are being performed annually in the United States, and it is projected that 1.26 million TKAs will be performed by the year 2030.¹ Simultaneously, there is a projected shortage of trained orthopaedic surgeons to care for these patients.² Telemedicine and innovative home-based technologies to monitor patient outcomes after surgery have gained increasing attention.³ This was possible due to the recent technological advances in telecommunication, allowing the development of commercially-available, easily-accessible, and low-cost home monitoring and virtual rehabilitation systems to allow clinicians to monitor the patient's adherence to post-operative rehabilitation and treatment protocols, particularly for relatively low-risk patients in which a normal recovery is expected.

Recently, emerging evidence has shown that home monitoring systems may have comparable efficacy to conventional follow-up clinic visits in monitoring patient progress postoperatively.⁴⁻⁷ Studies have also shown this technology may aid in lowering the cost of healthcare delivery to these patients while they are being monitored in real-time.^{8,9} In addition, it has been shown that postoperative interventions cost between 37% to 40% of the total episode payment for primary total joint arthroplasty.¹⁰ Therefore, with the recent paradigm shift from "volume-based" to "value-based" healthcare, the use of modern technology allowing optimal patient outcomes while decreasing cost becomes extremely relevant.¹¹

Objectives

In this pilot study, the objective was to assess a novel technology for postoperative home-based monitoring and communication for patients who underwent primary TKA. We specifically evaluated 1) the accuracy of patient mobility and knee range of motion (ROM) measurements obtained using home-based monitoring, and 2) the ability of the technology to monitor physical therapy compliance and collect patient-reported outcomes.

Eligibility

Data will be prospectively collected from a total of 10 patients over the age of 18 years who are scheduled for elective primary TKA. All enrolled patients must meet the following eligibility criteria.

Inclusion Criteria:

1. Scheduled for unilateral primary TKA
2. Reside within 75 miles (driving distance) from the hospital

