All patient-reported and functional measurements will be collected electronically via the in-home monitoring system at the intervals specified in the table below and manually by a clinician preoperatively, during one homecare visit per week, and at the 4, 8, and 12 week clinical follow-up visits. The Knee injury and Osteoarthritis Outcome Score (KOOS) consists of 5 subscales (Pain, other Symptoms, Function in daily living, Function in sport and recreation, and knee related Quality of life (QOL)). However, we will only assess KOOS Pain, Function (using the KOOS – Physical Function Shortform) and QOL for this study. Each section is scored independently from the others on a 0-to-100 transformed scale, where zero represents extreme knee problems and 100 represents no knee problems. Functional measures such as the maximum attainable ROM and the number of steps taken will be tracked using sensors worn by the patient. The ROM sensor values will be verified with range of motion measurements taken using a goniometer during therapy and MD visits. Patients will be asked to return all equipment at the time of their 12 week clinic visit.

Outcome Type	Scale	Frequency	
		Electronically Monitored	Collected at Follow-up Visit
Patient-Reported	KOOS Pain	qwk	q4wk
	KOOS Function	qwk	q4wk
	KRQoL	qwk	q4wk
	VAS Pain	tid	q4wk
Function Measure	ROM	tid	q4wk
	TUG	tid	q4wk
	Rehabilitation Compliance	qd	q4wk

qwk = every week; q4wk = every 4 weeks; tid = three times a day; qd = every day; KOOS = Knee injury and Osteoarthritis Outcome Score; KRQoL = knee related quality of life; VAS = visual analog scale; ROM= range of motion; TUG = timed up and go.

Statistical Analysis

A sample of 10 patients will be used as a proof of concept and can be used to refine future sample size calculations. Statistical analysis will be primarily descriptive. The Wilcoxon signed-rank test will be used to evaluate the agreements between the home-monitoring and clinician-based measurements to yield a concordance correlation coefficient that represents a measure of reliability of the method.

References

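### If the concordance coefficient is pooled over visits, recovery itself raises it, so it cannot stand for accuracy at a given visit; the plan does not say whether visits are pooled

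*Combined protocol and SAP*

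**What the plan says.** Objective 1 is to evaluate "the accuracy of patient mobility and knee range of motion (ROM) measurements obtained using home-based monitoring". The Statistical Analysis section has three sentences. The first sets the size: "A sample of 10 patients will be used as a proof of concept and can be used to refine future sample size calculations". The second reads "Statistical analysis will be primarily descriptive". The third states that "The Wilcoxon signed-rank test will be used to evaluate the agreements between the home-monitoring and clinician-based measurements", and that this is done "to yield a concordance correlation coefficient that represents a measure of reliability of the method".

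Data Collection has measurements taken electronically at home and also "manually by a clinician preoperatively, during one homecare visit per week, and at the 4, 8, and 12 week clinical follow-up visits". For ROM the comparison is explicit: "The ROM sensor values will be verified with range of motion measurements taken using a goniometer during therapy and MD visits". The table in the same section lists collection at follow-up visits as every four weeks only, against three times a day at home for ROM and timed up and go (TUG).

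The plan does not say which visits enter the coefficient, or whether it is computed per visit or over all visits. It names no method for repeated pairs, no limits of agreement and no threshold for acceptable reliability. It gives no ROM SD, recovery curve or expected sensor error.

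**The concern.** A concordance coefficient compares measurement error with the spread of true values in the data. After knee replacement the true values are expected to move over the weeks. If readings from different weeks go into one coefficient, that movement counts as true spread, and two methods that both follow it will score well even when they differ noticeably on any one day.

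Objective 1 asks about accuracy, and the coefficient is the only agreement estimate named for it. The signed-rank test looks for a systematic shift and does not measure the size of individual disagreements. A pooled value could therefore be taken as the sensor's accuracy at a visit, which is a different quantity. It would also depend on which weeks contributed, so it would not carry over to a later study with another schedule.

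**Working it through.** **Inputs from the documents.** 10 patients; clinician readings before surgery, weekly at homecare, and at weeks 4, 8 and 12 (text), or every four weeks (table). The sample size has no calculation behind it, so there is no figure of the plan's to reproduce.

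**Assumed inputs (none are in the documents).** No bias; between-patient SD of true ROM at a visit 8 or 10 degrees; error SD 5 or 7 degrees for each method; mean ROM by visit as shown below.

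**Formula.** Let B be the true variance between patients at a visit, T the variance of the visit means and E the error variance per method. With no bias and equal error variances:

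- within-visit concordance = B/(B+E)
- pooled concordance = (B+T)/(B+T+E)

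Equivalently, odds(pooled) = odds(within) × (1 + T/B). Whenever T exceeds zero, the pooled value is the higher one.

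**Variance of the visit means, T.**

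- Curve 1, weeks 4/8/12 at 90/105/115: mean 103.3, T = (177.8+2.8+136.1)/3 = 105.6
- Curve 2, weeks 4/8/12 at 100/112/118: mean 110, T = (100+4+64)/3 = 56
- Curve 2 with an early visit at 80: mean 102.5, T = (506.25+6.25+90.25+240.25)/4 = 210.75
- Flat curve, weeks 4/8/12 at 105/111/115: mean 110.3, T = (28.4+0.4+21.8)/3 = 16.9

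**Results at all four corners.**

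| SD, error | Within visit | Flat curve | Curve 2 | Curve 1 | Curve 2 + early visit |
|---|---|---|---|---|---|
| 8, 5 | 64/89 = 0.72 | 0.76 | 120/145 = 0.83 | 0.87 | 0.92 |
| 8, 7 | 64/113 = 0.57 | 0.62 | 120/169 = 0.71 | 0.78 | 0.85 |
| 10, 5 | 100/125 = 0.80 | 0.82 | 156/181 = 0.86 | 0.89 | 0.93 |
| 10, 7 | 100/149 = 0.67 | 0.70 | 156/205 = 0.76 | 0.81 | 0.86 |

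The effect of adding a visit must be read within Curve 2, where only the set of visits changes: 0.71-0.86 becomes 0.85-0.93.

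**What does not move.** The SD of paired differences is √2 × error SD, so the limits of agreement around zero bias are ±1.96 × √2 × 5 = ±13.9 degrees or ±1.96 × √2 × 7 = ±19.4 degrees in every column.

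**Second set of assumptions.** Take an exponential recovery curve, visits before surgery and at weeks 1, 2, 3, 4, 8 and 12, preoperative mean equal to the week-12 mean, between-patient SD 10 and SD of differences 10. Within-visit concordance is 0.67. Pooled over all visits it is 0.69, 0.75, 0.81 or 0.86 for a total rise of 10, 20, 30 or 40 degrees. Pooled over weeks 4, 8 and 12 only, it is 0.69, 0.71 or 0.73 for rises of 20, 30 or 40 degrees. With between-patient SD 15 and a 40-degree rise, the all-visit increase is from 0.82 to 0.90.

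**Precision with 10 patients.** In the same SD 10 case, a single-visit sample coefficient averages 0.60 (true value 0.67), with a 95% sampling range of about 0.10 to 0.89. Simulating the 10, 7 row, the coefficient computed after subtracting visit means also averages about 0.61 against a true 0.67.

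**The case against.** The strongest reply is that the plan never says visits are pooled. The indefinite article may simply name a type of statistic: the measures have different units, so one literal coefficient for everything is impossible. This stands. A reader might infer that the plan has chosen a single coefficient over the recovery course; the text is silent, so the point is conditional on pooling. Silence still matters, because the choice alone can move the reported value substantially and nothing in the plan rules pooling out.

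A reader might also infer that a moderately accurate sensor will look highly reliable, or that the coefficient would mostly measure recovery. The documents support neither. They contain no SD, recovery curve or sensor error, and values near 0.9 arise in only part of the assumed range. On Curve 1 with SD 10, recovery supplies 105.6 of 205.6 units of true variance, about half. If only weeks 4, 8 and 12 are paired, as the table may suggest, the rise can be slight. Nor do the documents give figures showing how far TUG, pain or the KOOS scales would behave like ROM.

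A pooled coefficient is also a legitimate value for the wider range of readings, and the study concerns monitoring over that range. That is right; the error would lie in reading it as accuracy at one visit.

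Finally, this overlaps with how repeated pairs are formed. One pair per patient at a named visit, or a coefficient per visit, would remove the effect. A clustered interval alone would not, because it leaves the point estimate unchanged.

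**Conclusion.** The concern holds in conditional form. The direction is algebraic: if visits are pooled and the true mean changes between them, concordance exceeds its within-visit value with the same sensor error. The size is not known from the documents. On the assumptions used, within-visit values of 0.57-0.80 become anything from 0.62-0.82 (flat curve, weeks 4, 8 and 12) to 0.85-0.93 (Curve 2 with an early visit), while the limits of agreement stay put.

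This is an analysis left unspecified where one available choice would mislead, rather than a stated error. It deserves a change even in a descriptive pilot of 10 patients, because the coefficient is the only named estimate for Objective 1 and the results may feed later sample size calculations.

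**What to change.** - For each measure, let the accuracy conclusion rest on bias and limits of agreement in its own units (degrees for ROM, seconds for TUG). Report them by recovery phase (for example before week 4, week 4, week 8, week 12) and overall, using a method that allows for repeated pairs within patient.
- Report the concordance coefficient as supporting information only, computed after subtracting each visit's mean. Average that mean over both methods, so that any bias between them is kept. Do not use a coefficient pooled across the recovery course as the reliability claim.
- Reconcile the text (preoperative and weekly homecare clinician readings) with the table (every four weeks), and state which visits contribute pairs, including whether a home reading exists to pair with the preoperative one.

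This costs a few sentences and no new data. The coefficient will be lower than a pooled one. It still depends on the spread among 10 patients and tends to run somewhat low at that size. Per-phase estimates will be imprecise and should be shown with intervals.
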